#### 5.8.4 Analysis of 12-Lead ECG

Summaries of 12-lead ECG parameters by treatment and visit will include:

- Descriptive statistics of actual and change from baseline.
- ECG status (i.e., normal, abnormal) summarized by a shift table
- Notable findings in ECG, which are defined as:
  - a new onset in the QT interval  $>500$  ms
  - a new onset in the QTcF interval  $>500$  ms
  - an increase from baseline in QTcF  $>60$  ms
  - an increase in heart rate from baseline by  $\geq 25\%$  for on-treatment values  $>100$  bpm
  - a decrease in heart rate from baseline by  $\geq 25\%$  for on-treatment values  $<50$  bpm
  - an increase in PR interval from baseline by  $\geq 25\%$  for on-treatment values  $>200$  ms
  - an increase in the QRS interval from baseline by  $\geq 10\%$  for on-treatment values  $>110$  ms, any time on treatment.

All the above tables will be presented through the Week 36 visit.

A listing will be provided for each participant by treatment and visit.

#### 5.8.5 Physical Examination

Results from physical examinations will be listed by participant and treatment at each visit.

### 5.9 Analysis of Pharmacokinetic Data

Descriptive summary tables (geometric mean, arithmetic mean, minimum, maximum, SD, and % coefficient of variation etc.) will be presented for the below categories by visit.

- Serum concentration for each treatment group
- PK concentration in ADA positive and ADA negative participants by treatment group
- Dose adjusted PK concentration in ADA positive and ADA negative participants

Following figures will be provided for the serum concentration data,

- Mean ( $\pm$ SD) serum concentration vs time profile: Linear scale
- Mean ( $\pm$ SD) serum concentration vs time profile: Semi-log scale
- Individual serum concentrations vs time profile: Linear scale
- Individual serum concentrations vs time profile: Semi-log scale

Serum concentration will be listed for each participant by treatment and visit.

## 5.10 Analysis of Pharmacodynamic Data

### 5.10.1 Handling of PD data based on the prohibited medication use

All the PD assessments (except OX40 occupancy on CD4+ T cell and OX40+/CD4+ T cell in CD4+ T cell) will be treated similar to the secondary efficacy assessment for handling the intercurrent event (prohibited medication). That is, all PD assessments after the start date of first prohibited medication use of each participant will be set to missing. The results for OX40 occupancy on CD4+ T cells and OX40+/CD4+ T cells within CD4+ T cells will be used as collected.

Statistical analysis of the following pharmacodynamic variables will be presented.

- Listing of RO (%) by visit for individual
- Table and figure of RO (%) over time for each dose group
- Listing of Percentage of OX40+/CD4+ T cell in CD4+ T cell (%) by visit for individual
- Table and figure of Percentage of OX40+/CD4+ T cell in CD4+ T cell over time for each dose group
- Listing of Olink target 48 cytokine panel proteins levels in serum (pg/mL), by visit for individual (45 proteins)
- Table and figure of Olink target 48 cytokine panel proteins levels in serum (pg/mL) log10 transformed change from baseline over time for each dose group (45 proteins)
- Listing of Olink target 48 immune surveillance panel proteins levels in serum (pg/mL), by visit for individual (44 proteins)
- Table and figure of Olink target 48 immune surveillance panel proteins levels in serum (pg/mL) log10 transformed change from baseline over time for each dose group (44 proteins)
- Figure of baseline Th1/Th2/Th17/Th22 fold change vs healthy subject for individual
- Figure of baseline, Week 16 and Week 24 Th1/Th2/Th17/Th22 fold change vs healthy subject for each dose group
- Table and figure of IgE (IU/mL) log10 transformed change from baseline over time for each dose group
- Listing of levels of IgE for individual
- Listing of OX40 positive cells (cells/mm^2) in biopsy by visit for individual
- Table and figure of Week 24 LS (Lesion) vs Week 16 LS vs baseline LS vs baseline NL (non-lesion) OX40 positive cells in biopsy for each dose group
- Listing of OX40L positive cells (cells/mm^2) in biopsy by visit for individual
- Table and figure of Week 24 LS vs Week 16 LS vs baseline LS vs baseline NL OX40L positive cells in biopsy for each dose group
- Listing of Tryptase positive cells (cells/mm^2) in biopsy by visit for individual
- Table and figure of Week 24 LS vs Week 16 LS vs baseline LS vs baseline NL Tryptase positive cells in biopsy for each dose group
- Listing of CD3 positive cells (cells/mm^2) in biopsy by visit for individual
- Table and figure of Week 24 LS vs Week 16 LS vs baseline LS vs baseline NL CD3 positive cells in biopsy for each dose group
- Listing of CD8 positive cells (cells/mm^2) in biopsy by visit for individual

- Table and figure of Week 24 LS vs Week 16 LS vs baseline LS vs baseline NL CD8 positive cells in biopsy for each dose group
- Listing of FcEpsilonR1 positive cells (cells/mm^2) in biopsy by visit for individual
- Table and figure of Week 24 LS vs Week 16 LS vs baseline LS vs baseline NL FcEpsilonR1 positive cells in biopsy for each dose group
- Listing of expression of KRT35 in biopsy by visit for individual
- Listing of H&E staining results description in biopsy by visit for individual

Additionally, further analysis of the pharmacodynamic variables, including RNAseq data and related considerations will be performed by [name] lab at Icahn School of Medicine at Mount Sinai and biomarker team at sponsor, which will be documented separately.

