Efficacy Analyses

Continuous efficacy variables will be summarized using descriptive statistics which will include mean, median, minimum, maximum, Q1 and Q3, and standard deviation. Categorical efficacy variables will be summarized by

frequency and percentage for each category. Analysis will be presented by cohort (dose group) as well as the overall population (two cohorts pooled) if efficacy results across various endpoints by dose group are similar. In general, efficacy analyses will be descriptive based on observed data. For the key efficacy endpoints based on SALT score, besides the descriptive analyses, additional analyses will be planned, including mixed model repeated measure (MMRM) analysis and one sample t-test for percent (%) changes and absolute changes from baseline in SALT over time (by visit) up to Week 24 by dose group and in the pooled population (if efficacy results across various efficacy endpoints by dose group are similar), to evaluate if these changes are nominally significant. Various imputation methods will also be explored in addition to the observed value method. Treatment policy-based estimand will be used for all efficacy analysis. Further details including handling of specific intercurrent events and other imputation methods will be specified in the prospective statistical analysis plan (SAP).

PK Analyses

Serum concentration data will be tabulated and summarized (geometric mean, arithmetic mean, minimum, maximum, SD and % coefficient of variation) by treatment group for each visit at which samples were taken.

Immunogenicity Analyses

The immunogenicity results will be summarized using descriptive statistics by the number and percentage of participants who develop detectable ADA. The incidence of positive ADA will be reported for evaluable participants. The effect of immunogenicity on PK, efficacy and safety may be evaluated if data allows.

PD Analyses

Biomarker data will be listed by participant and visit/timepoint.

Timing of analyses

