## 1. OVERVIEW

The purpose of the statistical analysis plan (SAP) is to ensure the credibility of the study results by pre-specifying statistical approaches for the analysis of this study. The SAP is intended to be a comprehensive and detailed description of strategy and statistical techniques to be used to realize the analysis of data for IMG-007-202. This SAP was written and finalized prior to the database lock, based on study protocol IMG-007-202 version 4 and 4.1(Canada only) (02 August 2024). Any methodological deviations from the protocol are documented. The analyses laid out in this SAP will be implemented by MeDaStats LLC for Inmagene Biopharmaceuticals.

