### 4.5.1 Secondary Efficacy Variable

The secondary efficacy endpoint is the percentage change in SALT from baseline to Week 24.

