#### 5.7.2.2 *Responder type (binary) efficacy endpoints*

The responder type (binary) endpoints will be reported using frequency and percentage by treatment along with the 95% Clopper-Pearson exact confidence interval for the proportion.

Based on the estimand framework introduced in [ICH E9\(R1\)](#), additional details relating to the definition of the estimand is proposed.

Handling of intercurrent events (for responder type binary endpoints) of treatment discontinuation and prohibited medication:

- *Treatment discontinuation*: Treatment policy strategy will be followed. i.e., all the collected data available after treatment discontinuation will be included in the analysis.
- *Any prohibited medication*: Participant will be reported as non-responder at all the visits occurring after the prohibited medication start.

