### **5.7.3 Analysis of Other Exploratory Efficacy Variables**

All the continuous exploratory variables will be analyzed using descriptive statistics (n, mean, median, standard deviation, minimum, and maximum).

All the binary exploratory variables will be summarized with frequency and percentages.

Intercurrent events will be handled as described in section [5.7.1](#) and [5.7.2.2](#) based on the characteristics of the analysis variable. No additional missing data imputations and sensitivity analysis are applicable for other exploratory endpoints.

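### SAP 5.10.1 indicates that SALT percent change is set to missing after a prohibited medication, which is neither the protocol's treatment-policy estimand nor the rule used for SALT30

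*SAP*

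**What the plan says.** The secondary endpoint is defined in SAP 4.5.1: "The secondary efficacy endpoint is the percentage change in SALT from baseline to Week 24". SAP 5.7.1 analyses it with a descriptive Week 24 summary and with an MMRM that tests the change at each visit against zero.

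The rule for prohibited medication on this endpoint is visible only through SAP 5.10.1. Apart from two OX40 measures, PD data "will be treated similar to the secondary efficacy assessment for handling the intercurrent event (prohibited medication", which the section spells out as "all PD assessments after the start date of first prohibited medication use of each participant will be set to missing".

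For binary endpoints, which include SALT30, SAP 5.7.2.2 says: "Participant will be reported as non-responder at all the visits occurring after the prohibited medication start". That section applies a treatment-policy strategy to treatment discontinuation only. SAP 5.7.3 carries the intercurrent-event rules of 5.7.1 and 5.7.2.2 to the other exploratory endpoints and adds: "No additional missing data imputations and sensitivity analysis are applicable for other exploratory endpoints".

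The protocol synopsis states: "Treatment policy-based estimand will be used for all efficacy analysis". It then defers detail: "Further details including handling of specific intercurrent events and other imputation methods will be specified in the prospective statistical analysis plan (SAP". SAP section 1 says: "Any methodological deviations from the protocol are documented".

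**The concern.** One event, the start of a prohibited medication, meets three rules. The protocol would use the SALT values collected afterwards. The SAP, by cross-reference, removes them from the percent change. For SALT30 the SAP replaces them with failure. The mean change and the responder rate can then disagree simply because they treat the same people differently.

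Much of the prohibited list consists of treatments for alopecia areata. The last dose is at Week 4 and the endpoint is at Week 24, which leaves 20 weeks in which a participant without regrowth might start one. If that happens, the loss of data is related to the outcome. There is no control arm in which a similar loss could offset it. At stake is what the Week 24 mean, and the continuous endpoints of SAP 5.7.3, actually estimate.

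**Working it through.** The documents give no figure to reproduce: the sample-size reasoning is redacted, and neither the number of users nor their SALT values are stated. The calculations below illustrate size under stated assumptions. From the documents: 6 participants in Cohort 1, 24 in Cohort 2, and seven post-baseline SALT visits up to Week 24 (Weeks 4, 6, 8, 12, 16, 20, 24).

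**Arithmetic of the observed-case mean.** Let k of N participants be users with Week 24 change u, and let the others have mean m. Setting users to missing gives m. Keeping them gives ((N − k)m + ku)/N. With u = 0 the relative inflation is N/(N − k) − 1, whatever m is. For Cohort 2, assuming m = −30%, the set-to-missing mean is always −30.0%:

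| Users k of 24 | Inflation if u = 0 | Mean, users kept at 0% | Mean, users kept at −60% |
|---|---|---|---|
| 1 | 24/23 − 1 = 4% | −28.8% | −31.3% |
| 2 | 24/22 − 1 = 9% | −27.5% | −32.5% |
| 3 | 24/21 − 1 = 14% | −26.3% | −33.8% |
| 4 | 24/20 − 1 = 20% | −25.0% | −35.0% |

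One user in Cohort 1 gives 6/5 − 1 = 20%. Three users in the pooled 30 give 30/27 − 1 = 11%. The last column shows that the direction reverses when users do better than the rest.

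**First simulation.** There were 300 trials of 24 participants. Half responded to −50%, and non-responders started other treatment before Week 16 or Week 20. The MMRM was represented by a maximum-likelihood multivariate normal mean. With 3 users, the mean with 0% assigned was −25.2. The observed mean was −28.8 (28.8/25.2 − 1 = 14%) and the likelihood mean −25.9 (25.9/25.2 − 1 = 3%). For 1, 2, 3 and 4 users the likelihood mean was inflated by 0.8, 1.5, 2.8 and 3.5%.

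**Second simulation.** There were 3,000 trials per scenario with 24 participants each. The mean Week 24 change without other treatment was about −25% (between-participant SD 25). Other treatment could start after Week 12, 16 or 20, and 12% to 17% of values were missing at Week 24. The other treatment added nothing, or 30 or 60 points of improvement per 12 weeks.

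| What drives use | Effect of other treatment | Without other treatment | Observed only | Likelihood model | All collected values |
|---|---|---|---|---|---|
| Last observed value | 0 | −25.1 | −28.3 | −25.1 | −25.1 |
| | 30 | −24.9 | −28.0 | −24.9 | −27.7 |
| | 60 | −25.0 | −28.1 | −25.0 | −30.6 |
| Next, unobserved value | 0 | −25.0 | −28.0 | −25.4 | −25.0 |
| | 30 | −24.9 | −28.0 | −25.4 | −27.4 |
| | 60 | −25.0 | −28.1 | −25.5 | −30.2 |
| Unrelated to response | 0 | −25.1 | −25.1 | −25.1 | −25.1 |
| | 30 | −24.9 | −24.9 | −24.9 | −28.4 |
| | 60 | −24.8 | −24.8 | −24.8 | −31.8 |

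Compared with the mean without other treatment, the observed-only mean is about 3 points too favourable when poor response drives use. The likelihood model is off by 0 to 0.5 point. Compared with all collected values, which is the protocol's estimand, the observed-only mean runs from about 3 points too favourable to 7.0 points less favourable (31.8 − 24.8). When the other treatment works, the likelihood model also differs from all collected values, by about 2 to 7 points, because it answers a different question.

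**The case against.** A reader might infer that the Week 24 SALT result drops everyone who turned to other treatment and is therefore too favourable. The documents do not support that, for four reasons.

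- **The governing text is withheld.** SAP 5.7.1 announces estimand details and then goes straight to line graphs. SAP 5.7.3 refers back to 5.7.1 for intercurrent events, and 5.7.2.1 refers to sensitivity analyses specified for the secondary endpoint. SAP section 5 allows descriptive counts to include imputed values. Set-to-missing may be only a first step for SALT percent change, and a mitigating analysis or a recorded deviation may already exist.
- **The MMRM does not drop these participants.** Their visits before the medication stay in the model.
- **The direction is not fixed.** The documents do not say why participants would start a prohibited medication. The list also covers live vaccines, biologics, systemic immunosuppressants, and newly started or changed statins or finasteride even when not used for alopecia. An effective other treatment reverses the sign.
- **Different strategies for a continuous score and a responder endpoint are not in themselves an error.** The stakes are also limited, because the primary objective is safety and the SALT p-values are nominal.

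These arguments defeat a claim of assured bias. They do not remove the conflict. Deferring detail to the SAP lets the SAP implement the stated estimand, not replace it silently. The MMRM's protection also depends on fitting 7 × 8/2 = 28 covariance parameters to about 30 participants. The fallbacks are simpler covariance structures and then ANCOVA, which, run visit by visit, uses only participants with a value at that visit.

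**Conclusion.** The point holds as an unreconciled estimand. The set-to-missing rule indicated in SAP 5.10.1 and the non-responder rule in 5.7.2.2 both differ from the treatment-policy estimand in the protocol synopsis, and no deviation is visible in the public text.

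The numerical consequence is conditional. Observed-case means in Cohort 2 would be about 4% to 20% too favourable in relative terms if 1 to 4 of 24 participants are users with about 0% change. They would be less favourable than treatment policy if the other treatment regrows hair. The favourable bias in the MMRM is small: about 1% to 3.5% relative in the first simulation and 0 to 0.5 point in the second. Every figure rests on assumed numbers of users and assumed SALT values.

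The effect is clearest for the continuous endpoints under SAP 5.7.3, which inherit the rule, are only described, and get no additional imputation or sensitivity analysis. For the secondary endpoint, confidence is moderate because the text of 5.7.1 is not visible.

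**What to change.** In SAP 5.7.1, carried to 5.7.2.1 and 5.7.3, state the prohibited-medication rule and either reconcile it with the protocol's estimand or record the deviation. Unless the withheld text already provides them, add beside the set-to-missing analysis:

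1. The Week 24 descriptive summary and MMRM on all collected SALT values, as the protocol's estimand requires.
2. An analysis that assigns 0% change from the start of a prohibited treatment for alopecia areata, in line with the SALT30 failure rule. That rule covers any prohibited medication, so the SAP should say which medications trigger the 0% assignment.

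Report the number of users by cohort and visit, so that a reader can see whether the issue matters at all.

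The cost is SAP wording and two more runs of an existing table. No new data are needed for participants who remain in the study, because the SALT visits are already scheduled. The 0% analysis may look slightly less favourable. With no control arm, the all-data analysis may credit regrowth from another treatment to IMG-007. The analyses should therefore be read together.

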## 5.11 Analysis of Immunogenicity Data

The ADA variables will be summarized using descriptive statistics by treatment in the immunogenicity analysis set. Frequency tables of the proportion of participants developing ADA positivity in the ADA assay, pre-existing ADA, treatment-emergent, treatment-boosted, persistent, indeterminate and transient ADA responses will be presented as absolute occurrence (n) and percent of participants (%), presented by treatment groups.

A listing of ADA data will be provided. The number and percentage of participants with ADA positive at each visit will be presented in the listing. The percentage will be based on the number of participants with ADA assessment at each visit.

The following summaries will be performed on the immunogenicity analysis set:

- Number (%) of patients negative ADA at all the time points analyzed by treatment group
- Number (%) of patients ADA positive at time points analyzed by treatment group
- Number (%) of patients with pre-existing ADA, treatment-emergent ADA, and treatment boosted ADA response by treatment group
- Number (%) of patients with persistent, transient and indeterminate treatment-emergent ADA response by treatment group
- Descriptive statistics of PK concentration in ADA positive and ADA negative participants by treatment group
- Descriptive statistics of dose adjusted PK concentration in ADA positive and ADA negative participants

## 6. DATA CONVENTIONS

The following analysis conventions will be used in the statistical analysis.

### 6.1 Definition of Baseline for Efficacy/Safety Variables

Unless otherwise specified, the baseline assessment for all measurements will be the latest available valid measurement taken prior to the administration of study drug (Week 0 (Day 1)).

When it is not possible to determine the time of assessment, baseline value would be determined based on the measurement recorded on the day administration of the first dose of IMP.

## 6.2 Missing Data Handling

Missing data will not be imputed in listings. This section includes the methods for missing data imputation for some summary analyses, if necessary.

### *Adverse event*

If the intensity of a TEAE is missing, it will be classified as “severe” in the frequency tables by intensity of TEAE. If the assessment of relationship of a TEAE to the investigational product is missing, it will be classified as “related” in the frequency tables by relation to the investigational product.

The partial date values will be imputed as specified in the [Appendix 11.2](#). Imputed dates will not be presented in the listings.

## 6.3 Analysis Visit Window

For summaries that include data collected over multiple visits, where appropriate, the data will be summarized by analysis visit window. If there are multiple measurements within a scheduled visit window (refer [Appendix 11.3](#)), the closest measurement to the scheduled timepoint of the visit will be used in the analysis. If there are two observations which have the same difference in days to the planned day, but which are not measured on the same day, the later value will be selected. If there is more than one observation on the same day, then;

- Latest value will be considered in all cases except for vital signs, ECG.
- Average value will be considered in cases of vital signs and continuous ECG values.
- The worst value will be considered for ECG interpretation.

[figure not shown]
For PK and ADA data, if multiple measurements are taken within a scheduled visit window, the earliest value will be used for the analysis.

All measurements will be presented in the listing.

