7.2.3 Vital Signs and Physical Examination

Vital signs will be measured in semi-supine or supine position after 5 minutes of rest and will include temperature, respiratory rate, systolic and diastolic blood pressure, and pulse rate. Vital sign assessments can be repeated at the discretion of the PI or designee.

A complete physical examination will include, at a minimum, assessments of the skin, head and neck, cardiovascular, respiratory, gastrointestinal, and neurological systems. Height and weight will also be measured and recorded. Please refer to the SoA (Table 1) as to when the assessments are required.

A brief physical examination will include, at a minimum, assessments of the skin, lungs, cardiovascular system, and abdomen (liver and spleen). Symptom-directed physical examinations will

be completed at each follow-up (including the extended follow-up) visit at the discretion of the investigator.

Investigators will be instructed to pay special attention to clinical signs related to previous serious illnesses. Unscheduled physical examinations can be conducted at the discretion of the PI or designee.

7.2.4 12-Lead Electrocardiogram

The investigator or designee will perform ECG examinations at the timepoints listed in the SoA (Table 1).

Heart rate and PR, QRS, QT, and QTc intervals, etc., will be measured. Triplicate ECG will be taken if there are any clinically significant abnormalities detected by the physician in a single ECG.

Resting 12-lead ECGs should be recorded after the participant has been semi-supine or supine for a minimum of 5 minutes. ECGs will be interpreted on-site by the investigator to ensure participant safety. The PI (or designee) will evaluate the ECGs tracings to determine if they are normal, or if there are any clinically significant abnormalities. Site standard ranges will be used to determine if any parameters are considered out of range. ECGs can be repeated at the discretion of the PI or designee.

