### 11.3 Analysis Visit Window

Analysis Visit	Target Day	Group 1	Group 2	Group 3	Group 4	Group 5*	Group 6	Group 7
Baseline	1	Up to day 1	Up to day 1	Up to day 1	Up to day 1	Up to day 1	Up to day 1	Up to day 1
Week 1	8	2-11	-	-	-	-	-	-
Week 2**	15	12-25	2-25	2-25	2-25	-	-	2-25
Week 4	29	26-36	26-36	26-71	26-43	2-36	-	>25
Week 6	43	37-50	37-50	-	-	37-50	-	-
Week 8	57	51-71	51-71	-	44-71	51-71	-	-
Week 12	85	72-99	72-99	-	72-99	72-99	-	-
Week 16	113	100-127	100-127	72-141	100-127	100-127	2-141	-
Week 20	141	128-155	128-155	-	128-155	128-155	-	-
Week 24	169	156-190	156-190	142-211	156-211	156-190	142-190	-
Week 30	211	191-232	-	-	-	191-232	191-232	-
Week 36	253	233-274	-	212-274	212-274	233-274	233-274	-

Group 1: Vital signs, Physical examination, Adverse events, Prior and concomitant therapies, Hematology, blood chemistry, PK sampling.

Group 2: ADA sampling

Group 3: Urinalysis

Group 4: Pregnancy test

Group 5: SALT, IATS, IGA-EB, IGA-EL, IGA-FN, PGIS-AA, PGIS-S, PGIS-EB, PGIS-EL, PGIS-FN, AAPPO, HADS

Group 6: ECG, TB testing and TB risk follow up

Group 7: Study treatment administration

\*Use group 5 for PD blood sample by removing week 6 and changing the Week 4 window from “2-36” to “2-43” and Week 8 window from ’51-71’ to “44-71”.

\*\* The upper bound of window period extended by 3 days to accommodate the unscheduled Week 2 assessments.

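### In the by-visit table of notable ECG findings, an abnormal unscheduled ECG during dosing is replaced by the Week 16 ECG

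*SAP*

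**What the plan says.** Four parts of the plan act together.

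- **Layout.** SAP 5.8.4 opens with "Summaries of 12-lead ECG parameters by treatment and visit will include" and lists the notable findings beneath it: QT or QTcF above 500 ms, a QTcF rise above 60 ms, and heart rate, PR and QRS criteria. Only the QRS criterion carries a qualifier that it applies at any time on treatment.
- **Selection.** When a window holds more than one measurement, SAP 6.3 states that "the closest measurement to the scheduled timepoint of the visit will be used in the analysis". If two different days are equally distant, "the later value will be selected". For several readings on the same day, "Average value will be considered in cases of vital signs and continuous ECG values", and "The worst value will be considered for ECG interpretation".
- **Windows.** Appendix 11.3 defines "Group 6: ECG, TB testing and TB risk follow up". For this group, Baseline runs up to Day 1, and the next window is Week 16, target Day 113, covering Day 2 to Day 141.
- **Extra ECGs.** Protocol 7.2.4 provides that "ECGs can be repeated at the discretion of the PI or designee" and calls for triplicates when a single ECG shows a clinically significant abnormality. More than one ECG per window is therefore foreseeable.

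**The concern.** Unscheduled ECGs tend to be recorded because something looks wrong. No routine ECG is scheduled between Baseline and Week 16, so an unscheduled one is the only ECG information on the dosing period after baseline. The selection rule favours whichever ECG is nearest Day 113, so the routine late ECG represents the whole stretch that contains the second and third infusions. The notable-findings table could then show no QTcF above 500 ms while the listing shows one.

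The SAP handles comparable data differently. SAP 5.8.2 takes the worst CTCAE grade per laboratory parameter, SAP 5.8.1 takes the maximum severity of adverse events, and SAP 6.3 itself takes the worst ECG interpretation within a day. Across days within a window, the ECG rule is not a worst-value rule.

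**Working it through.** **Inputs.** Target days 113, 169, 211 and 253, and the Day 2–141 window (SAP 11.3). Visit tolerance ±3 days, so a Week 16 ECG falls on Days 110–116 (schedule of assessments). Infusions on Days 1, 15 and 29 (Protocol 6.4). Selection by the smallest |day − 113|, with the later day on ties (SAP 6.3).

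**1. The plan's own window.** Midpoints of adjacent targets are (113 + 169)/2 = 141, (169 + 211)/2 = 190 and (211 + 253)/2 = 232. All three match the printed bounds, so Day 2–141 is the intended window and not a misprint. It spans 141 − 2 + 1 = 140 days.

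**2. An unscheduled ECG around dosing.**

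| ECG day | Distance from Day 113 | Largest distance of a Week 16 ECG | ECG kept |
|---|---|---|---|
| 15 | 98 | 3 | Week 16 |
| 29 | 84 | 3 | Week 16 |
| 36 | 77 | 3 | Week 16 |

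The result is the same for every Week 16 date from Day 110 to Day 116. With Week 16 done on Day 113, all 140 − 1 = 139 other days in the window lose. The ECG kept is taken 113 − 29 = 84 days, or 12 weeks, after the planned last dose. The unscheduled ECG is used only if it is the sole or nearest ECG in the window.

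**3. An ECG after the first infusion on Day 1.** The post-baseline windows start on Day 2. SAP 6.1 takes baseline from before administration, so an ECG known to follow the infusion is not the baseline value either. It enters no by-visit summary as a post-baseline value.

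**4. Repeats on a later day.**
- *Both ECGs on or before Day 113:* the later one is always nearer, so it displaces the earlier. As an assumed example, a QTcF of 505 ms on Day 110 (distance 3) repeated at 470 ms on Day 112 (distance 1) is reported as 470 ms.
- *Abnormal ECG on or after Day 113:* any later day is farther away, so the abnormal value stays.
- *Scheduled ECG on Days 110–116, repeated 1 to 7 days later:* there are 7 × 7 = 49 combinations. The repeat displaces the first ECG in 6 (Day 110) + 4 (Day 111) + 2 (Day 112) = 12 of them, and in none from Day 113 onward.

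**5. Repeats on the same day.** Continuous values are averaged rather than dropped. Assumed QTcF readings of 505, 492 and 494 ms give 1491/3 = 497 ms, which falls under the 500 ms threshold. The interpretation still takes the worst reading.

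**6. Size of one missed participant.** 1/6 = 16.7% of Cohort 1, 1/24 = 4.2% of Cohort 2, 1/30 = 3.3% overall.

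**The case against.** The strongest reply is that very little can be lost. Protocol 8.2.3.1 requires an ECG result to be reported as an adverse event if it is clinically significant, leads to intervention or changes study treatment, so such a finding reaches the TEAE tables whatever the windows do. SAP 6.3 keeps every measurement in the listings, and about 30 participants can be read through by eye. All of this stands. It leaves exposed the threshold crossing that met none of those reporting conditions, and thresholds are tabulated partly to capture such cases independently of investigator judgement.

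A second reply is that SAP 6.3 leaves room: "where appropriate, the data will be summarized by analysis visit window". That is true, but nothing exempts notable findings, and the lead-in to SAP 5.8.4 places them by visit. The QRS qualifier points the other way for one criterion only, so the section conflicts with itself.

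A third is that the wide window merely follows from a schedule with no ECG between Baseline and Week 16. That is right, and the window is sound for by-visit means. The difficulty arises only when it also decides which abnormal values are counted. Nor does the protocol prescribe an ECG for an infusion reaction, so the dosing-day cases are possible rather than planned.

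Three stronger readings are tempting and are not supported:
- *That any abnormal ECG later repeated drops out.* It does so only if the repeat is nearer Day 113, or tied and later; same-day repeats are averaged.
- *That the primary safety analysis is compromised.* The primary endpoint is the incidence of TEAEs, not an ECG table.
- *That the interim and safety review committee outputs share the defect.* SAP 7.1.1 and 11.5 do not say that those ECG outputs are by visit; for the interim output, the rule on which ECGs count is simply unstated.

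**Conclusion.** The point holds for the notable-findings table in SAP 5.8.4. Under the stated rules, an abnormal unscheduled ECG in the dosing period is displaced whenever a Week 16 ECG exists, and a post-infusion Day 1 ECG has no post-baseline place. An abnormal ECG before Day 113 can also be displaced by a repeat nearer that day. This is a stated rule that could give a wrong count, not merely missing detail.

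The consequence is limited to a descriptive summary. The percentages in step 6 are the weight of a single event, not an estimate of loss, because the number of unscheduled ECGs is unknown. The conclusion assumes that SAP 6.3 is applied to notable findings as written and that the participant has a Week 16 ECG. It should be corrected because the remedy is small and brings ECG counting into line with the SAP's laboratory rule.

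**What to change.** In SAP 5.8.4, alongside the by-visit table, add a count and percentage of participants who meet each notable-finding criterion at any time after the start of the first infusion. Count each participant once per criterion, and use all scheduled, unscheduled, repeat and Day 1 post-infusion ECGs. State in the same place whether same-day replicates are tested singly or as their average, since step 5 shows that the answer can differ. This also resolves the inconsistency in the QRS criterion.

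In SAP 7.1.1, state that the interim proportion of participants with notable ECG findings uses the same any-time definition.

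Keep the Appendix 11.3 windows and the SAP 6.3 selection rule for by-visit descriptive statistics and the by-visit shift table. Replacing the shift table with a worst-post-baseline version would be a preference and is not needed here.

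The cost is a few sentences of SAP text and slight extra programming, with no new data. The number of notable findings reported may rise slightly.
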